## **7.2.      Definition of a Serious Adverse Event (SAE)**

An SAE is defined as any event that meets the following criteria:

- It results in death or is life-threatening (i.e., presents an immediate risk of death from the event as it occurred). (This criterion is not intended to include an AE that, had it occurred in a more severe form, might have caused death.)
- It results in persistent or substantial disability or incapacitation. (This criterion is not intended to include experiences of relatively minor medical significance, such as uncomplicated headache, diarrhea, or sprained ankle.)
- It results in hospitalization.
- It results in prolongation of an existing hospitalization.
- It is a congenital anomaly or birth defect.
- It requires medical or surgical intervention to prevent any of the above outcomes.

Medical and scientific judgment should be exercised in determining whether an AE is serious when considering important medical events that may not be immediately life-threatening or result in death or hospitalization, but may jeopardize the subject or may require intervention to prevent any of the other outcomes listed. Examples of such medical events that may also be considered serious include, but are not limited to, intensive treatment in an emergency room or at home for allergic bronchospasm, blood dyscrasias, or convulsions that do not result in hospitalization.

Hospitalization for elective treatment of a preexisting condition that did not worsen from baseline does not meet the definition of an SAE.

Social or convenience admission to a hospital or prolongation of a hospitalization for social or convenience reasons not associated with the occurrence of an AE does not meet the definition of an SAE.

### **7.2.1.    SAEs That Occur Before Administration of Study Medication**

Before administration of study medication, only SAEs assessed by the investigator as related to study participation (e.g., related to study procedures or a change in existing therapy) will be transcribed onto the SAE reporting form and reported to the sponsor.

### **7.2.2.    SAEs That Occur After Study Completion**

If an Investigator becomes aware of an SAE or death that occurs in a subject more than 30 days after the subject receives study medication and that investigator considers the event to be related to the study medication, the investigator is obligated to report the SAE to the sponsor.

### **7.3. Definition of a Suspected Adverse Reaction (SAR)**

A SAR is defined as any adverse event for which there is a reasonable possibility that the adverse event was caused by the study drug. For the purposes of IND safety reporting, 'reasonable possibility' means there is evidence to suggest a causal relationship between the drug and the adverse event. A suspected adverse reaction implies a lesser degree of certainty about causality than adverse reaction, which means any adverse event caused by a drug.

### **7.4. Definition of a Serious Suspected Adverse Reaction (SSAR)**

A SSAR is any Suspected Adverse Reaction that is determined to be serious, based on the outcomes of a SAE described in Section 7.2; i.e. death, life-threatening, causes or prolongs inpatient hospitalization, causes a persistent or significant incapacity or substantial disruption of the ability to conduct normal life functions, or a congenital abnormality/birth defect.

### **7.5. Recording and Evaluating Adverse Events and Serious Adverse Events**

It is the responsibility of the Investigator to collect all adverse events (AEs), serious and non-serious, derived by spontaneous, unsolicited reports of subjects, by observation and by routine open questionings e.g., "How have you felt since I last saw you?"

For randomized and enrolled patients, AEs will be captured from the time of signing of Informed Consent Form until End of Study or Early Termination. Adverse events/ Serious Adverse Events (SAEs) should be followed to resolution, stabilization, or until 30 days after the last dose of the study drug upon which patients will be referred to their primary medical provider for follow-up.

All adverse events, including observed or volunteered problems, complaints, or symptoms, are to be recorded on the appropriate eCRF.

Subjects should be instructed to report any adverse event that they experience to the Investigator, after signing the Informed Consent. Investigators should make an assessment for adverse events at each visit and record the event on the appropriate adverse event eCRF.

Pre-existing conditions will be recorded in the subject's source record and eCRF on the Medical History or appropriate page.

A treatment-emergent AE (TEAE) will be defined as an AE that begins or that worsens in severity after at least one dose of study drug has been administered.

Clinically significant abnormal laboratory or other examination (e.g., ECG) findings that are detected during the study or are present at baseline and significantly worsen during the study should be reported as adverse events.

The Investigator will exercise his or her medical and scientific judgment in deciding whether an abnormal laboratory finding or other abnormal assessment is clinically significant. Significant abnormal laboratory values occurring during the clinical study will be followed until repeat tests return to normal, stabilize, or are no longer clinically significant. The Investigator will attempt to establish a diagnosis of the event on the

basis of signs, symptoms, or other clinical information. In such cases, the diagnosis, not the individual signs or symptoms, should be documented as the AE or SAE.

Adverse event reporting will extend from signing of informed consent until End of Study visit /Early Termination visit. All AEs, regardless of the relationship to study drug, will be recorded in the subject source record and eCRF. Standard medical terminology should be used when describing AEs. The anatomical location of the AEs must be specified where applicable.

### **7.5.1. Assessment of Intensity**

The Investigator will make an assessment of intensity for each AE and SAE reported during the study, using his or her clinical judgment. The intensity of each AE and SAE recorded in the CRF should be assigned to one of the following categories:

- mild: an event that is easily tolerated by the subject, causes minimal discomfort, and does not interfere with everyday activities
- moderate: an event that is sufficiently discomforting to interfere with normal everyday activities
- severe: an event that prevents normal everyday activities

An AE that is assessed as severe should not be confused with an SAE. *Severity* is a term used to describe the intensity of a specific event, and both AEs and SAEs can be assessed as severe. The event itself, however, may be of relatively minor medical significance (such as a severe headache). This is not the same as *serious*, which is based on the subject's or event's outcome or on action criteria usually associated with events that pose a threat to a subject's life or functioning (see Section 7.2).

### **7.5.2. Assessment of Causality**

The investigator is obligated to use his or her clinical judgment to assess the relationship between the study medication and the occurrence of each AE or SAE. The investigator will assess the relationship to the study medication by using the following criteria:

- **Definitely Related:** An AE has a strong temporal relationship to the study drug. The AE is most likely explained by study drug. Dechallenge and rechallenge (if possible) are positive. The AE is consistent with a known response to the study drug. Another etiology is unlikely or significantly less likely.
- **Probably Related:** An AE has a strong temporal relationship to the study drug. The AE is more likely explained by study drug than by another cause. Dechallenge (if performed) is positive.
- **Possibly Related:** An AE has a reasonable temporal relationship to study drug. The AE could have been due to another equally likely cause. Dechallenge is positive.
- **Not Related:** The subject did not receive the study drug **OR** the AE has no temporal relationship to study drug **OR** the AE has a much more likely alternate

etiology **OR** the AE is due to an underlying or concurrent illness or effect of another drug.

Even in situations in which minimal information is available for the initial SAE report, it is important that the investigator always make an assessment of causality for every event before transmitting the SAE reporting form and completing the AE CRF page(s). The causality assessment is one of the criteria used when determining regulatory reporting requirements. The investigator may change his or her opinion of causality in light of follow-up information and amend the SAE reporting form and AE CRF page(s) accordingly.

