### **8.6. Safety and Tolerability Evaluations**

#### **8.6.1. Extent of Exposure**

All subjects will be expected to receive a single dose of study medication. No formal evaluation of the extent of exposure will be performed.

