9.2 Adverse Events

Treatment-emergent AEs are defined as AEs that start or worsen in severity after the first exposure to study medication through the Day 7 visit. Verbatim terms used by investigators to identify AEs in the CRFs will be mapped to the appropriate preferred (PT) and system organ class (SOC) using a standardized coding dictionary (MedDRA Version 21.0 or higher). All coding will be reviewed prior to database lock. All recorded AEs will be listed, but only TEAEs will be summarized.

Statistical Analysis Plan Version: 2.0

Effective Date: 08OCT2018

In addition to a listing of all TEAEs, separate listings of subjects with SAEs and listings of subjects with severe, treatment related, and AEs leading to premature discontinuation will be provided.

An overall summary will be prepared giving for each treatment group, all DFN-15 groups combined and overall of both the number of events and the number of subjects with TEAEs, SAEs, TEAEs by severity, TEAEs by relationship to treatment, and TEAEs leading to premature discontinuation.

The incidence of TEAEs will be summarized for each treatment group by SOC and PT within SOC (sorted in descending order by overall frequency). These summaries will be given in separate tables for the following categories of TEAEs:

- All TEAEs
- TEAEs leading to premature discontinuation
- SAEs

Also summarized will be TEAEs by maximum severity and by maximum relatedness to treatment. Adverse events will be deemed treatment related if they were recorded as probably, possibly, or definitely related.

If a given subject experiences a TEAE that maps to the same PT more than once, the subject will be counted once for the PT at its greatest severity (i.e., mild, moderate, or severe) and causality (i.e., attribution to study medication).

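### The weakest related category, *Possibly Related*, demands a positive dechallenge without exception, so after a single dose some unresolved events fit no causality category

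*Protocol*

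**What the plan says.** Protocol 7.5.2 gives four causality categories and tells the investigator to apply clinical judgment through them.

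- *Definitely Related*: strong timing, drug the most likely explanation, and "Dechallenge and rechallenge (if possible) are positive".
- *Probably Related*: strong timing, "The AE is more likely explained by study drug than by another cause", and "Dechallenge (if performed) is positive".
- *Possibly Related*: reasonable timing, then "The AE could have been due to another equally likely cause. Dechallenge is positive".
- *Not Related*: any one of four limbs. These are that no drug was received; that there is no temporal relationship; that "the AE has a much more likely alternate" etiology; or that the event is due to another illness or another drug.

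There is no *unlikely* or *unassessable* category. On timing, the section adds that "it is important that the investigator always make an assessment of causality for every event before transmitting the SAE reporting form", even when little is known, and Protocol 7.7 allows 24 hours for that form. On exposure, Protocol 8.6.1 states: "All subjects will be expected to receive a single dose of study medication". On analysis, SAP 9.2 states: "Adverse events will be deemed treatment related if they were recorded as probably, possibly, or definitely related".

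**The concern.** A causality scale should ask for less evidence as it moves from definite to possible. Here the dechallenge condition is conditional for *Probably* and absolute for *Possibly*, and no reason is given. It reads like a dropped qualifier.

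The single-dose design makes the omission matter. Nothing can be withdrawn, so the most that a positive dechallenge could mean is that the event went away as the drug cleared. An event still present at assessment cannot show that. Competing causes are built into the trial: every subject has just had oral surgery, and Protocol 5.15 permits oxycodone/acetaminophen rescue.

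At stake are the relatedness split in the safety tables, which serve the secondary objective of tolerability and safety, and the consistency of the investigator's causality call. Protocol 7.3 defines a suspected adverse reaction by a reasonable possibility of causation and asks for no dechallenge. On this point the scale in 7.5.2 is stricter than the protocol's own definition.

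**Working it through.** No arithmetic applies. The check takes one test case through the four definitions in Protocol 7.5.2.

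**Test case.** The subject received study drug. The timing is reasonable. Another cause is equally likely. The event is unresolved when assessed.

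| Category | Attribution condition | Dechallenge condition | Result |
|---|---|---|---|
| Definitely | Drug is the most likely explanation: not met | Positive, with an *if possible* qualifier | Fails on attribution |
| Probably | Drug more likely than another cause: not met | Positive only if performed | Fails on attribution |
| Possibly | Another equally likely cause: met | Positive, no qualifier: not met | Fails on dechallenge alone |
| Not Related | Any of four limbs (below) | None | Fails |

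**Limbs of *Not Related*.**
1. Drug not received: false.
2. No temporal relationship: false.
3. Alternative much more likely: false, because it is only equally likely.
4. Event due to another illness or drug: not established. Calling a cause equally likely does not say that the event is due to it.

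None of the four categories fits.

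**Which condition causes the gap.** Put the *Probably* qualifier into the *Possibly* line and change nothing else. Where dechallenge was not performed, the test case then fits *Possibly Related*. The missing qualifier is therefore the cause.

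**Limits of the gap.** If clearance of the single dose is accepted as a dechallenge, an event that has resolved can qualify as *Possibly Related*. The gap then covers events unresolved at assessment, including those that stay so. Protocol 7.5.3 lists not resolved and fatal among the outcomes, and such events can never show a positive dechallenge.

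**What a site might do, and what the tables would show.**
- Record *Not Related*: the event leaves the treatment-related summary in SAP 9.2.
- Record *Possibly* anyway: it is counted as related, as presumably intended.
- Move it up to *Probably*: it is counted as related, but the maximum-relatedness table overstates the degree.
- Leave it blank: it is analyzed as related (SAP 9.2; Protocol 8.3.2), although 7.5.2 asks for an assessment of every event.

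One of the four responses lowers the related count. The others leave it unchanged.

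**The case against.** The missing qualifier cannot be disputed, but several things limit its reach.

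- **The contrast with *Definitely* is uncertain.** In that line the qualifier follows the word rechallenge and may apply to it alone. This stands. The point rests on the contrast with *Probably*, which is clear.
- **Judgment could fill the gap.** A sensible investigator may treat the dechallenge sentence as inapplicable after one dose and choose *Possibly*. Some will. But the protocol directs that judgment through the listed criteria, so the result depends on the site.
- **Causality can be amended, and events are followed up** (Protocol 7.5, 7.5.2 and 7.6). This stands for events that later resolve, so the 24-hour report does not fix what the final tables show. It does not help events that never resolve.
- **The CRF guide and SAE form are not among the documents.** They may already allow a not-applicable entry. This stands as a reason to check them.

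Three stronger readings are tempting, and the documents do not support them.

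- *Related events are undercounted.* Only one of the four site responses has that effect, and SAP 9.2 tabulates all TEAEs regardless of relatedness.
- *Serious events escape reporting.* Protocol 7.7 sends every SAE during the study to the sponsor within 24 hours whatever its relationship. Under 7.8 the sponsor reports to authorities, and 7.5.2 calls investigator causality only one of the criteria. For SAEs learned of more than 30 days after dosing, Protocol 7.2.2 does make the duty depend on relatedness, but Appendix D frames that duty by reasonable possibility, without dechallenge.
- *This is the ordinary case, or covers most SAEs.* The documents give no AE rate, SAE rate or time to resolution.

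**Conclusion.** The point holds as a wording defect in the safety classification. Read literally, Protocol 7.5.2 leaves no category for an unresolved event with reasonable timing and an equally likely other cause. The consequence is possible inconsistent or wrong classification of relatedness, in two places: the descriptive treatment-related summaries of SAP 9.2, and the investigator's causality input to regulatory reporting. How many events are affected cannot be derived.

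The conclusion assumes that sites apply the criteria as written, and that neither the CRF guide nor the SAE form already supplies the missing option. Safety is summarized without statistical testing, and no efficacy analysis or decision rule depends on this scale. The correction is worth making because the stated rule is wrong as it stands and costs almost nothing to repair.

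**What to change.** In Protocol 7.5.2, replace the last sentence of *Possibly Related* with: *Dechallenge (if performed) is positive, or is not applicable or not yet known after a single dose.* Add that an unresolved event is not by itself a negative dechallenge. Check that the CRF completion guide and the SAE form carry the same wording. The grouping in SAP 9.2 can stay as it is.

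The cost is one revised sentence and one added sentence in the protocol, plus a check of two site documents. The small downside is that the treatment-related count may rise slightly.

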### **7.5.3. Assessment of Outcome**

All SAEs must be followed until they are resolved, the condition stabilizes, the events are otherwise explained, or the subject is lost to follow-up. The investigator will assess the outcome of the event by using the following terms:

- **Recovered/Resolved:** The event resolved or the subject recovered without sequelae. An event (either serious or non-serious) occurred and had an endpoint, and the subject experienced no restrictions. Examples include stent placement for coronary artery disease (a device implanted is not a sequela), an appendectomy (a scar is not a sequela), a postoperative wound infection, or an upper respiratory tract infection.
- **Recovered/Resolved with sequelae:** The event has at least one secondary outcome that may result in permanent disability, functional limitation, or both. Such sequelae are usually limited to SAEs. Examples include hip replacement resulting in foot drop (foot drop is not the intended outcome but is a risk of surgery), stroke resulting in paralysis, or emboli formation after a bacterial infection resulting in a renal infarct and loss of renal function.
- **Not Recovered/Not resolved:** At the end of the study, a non-serious event either has not changed in intensity or may not have recovered to baseline values, and the outcome is unknown. Examples include headache, low-grade fever, or nausea.
- **Unknown:** The subject has withdrawn from the study prematurely or is lost to follow-up, and the status of the event is unknown.

- **Fatal**

### **7.5.4. Assessment of Expectedness**

For the purposes of IND safety reporting, adverse events and suspected adverse events should be assessed as being expected or unexpected. An AE or SAR is considered unexpected if it is not listed in the investigator brochure or is not listed at the specificity or severity that has been observed; or, if an investigator brochure is not required or available, is not consistent with the risk information described in the general investigational plan or elsewhere in the current application.

## 7.6. Follow-up of Adverse Events and Serious Adverse Events

Non-serious AEs will be followed after the last scheduled study visit, until an appropriate resolution can be documented.

After the occurrence of an AE or SAE, the investigator is required to follow each subject proactively and provide further information on the subject's condition. All AEs and SAEs documented at a previous visit or contact are designated as ongoing and will be reviewed at subsequent visits or contacts.

SAEs will be followed until the event resolves, the condition stabilizes, the event is otherwise explained, or the subject is lost to follow-up. The investigator will ensure that follow-up information provided to the sponsor includes results of any additional laboratory tests or investigations, histopathologic examinations, or consultations with other healthcare professionals that serve to clarify the nature of the event, the cause of the event, or both.

New or updated information will be recorded on the originally completed SAE reporting form and entered into the CRF pages, with all changes signed and dated by the investigator. The updated SAE reporting form should be resubmitted to the sponsor within the time frames outlined in Section [7.7](#).

**SERIOUS ADVERSE EVENT REPORTING INSTRUCTIONS**

[name], Inc.

North American Pharmacovigilance Center

Email ID: **[contact]**

US Toll-Free [contact]**

Local US [contact]**

SAE Reporting Instructions:

1. All SAEs must be reported immediately (within 24 hours of becoming aware of the event). Please email the signed, scanned copy of the completed SAE form to **[contact]** and **[contact]** or fax the completed SAE form to [contact]**.
2. An email acknowledgement of receipt of SAE will be sent to the reporting site within one business day.

In the initial e-mail, the investigator must provide to the sponsor the following CRF pages, completed to the greatest extent possible:

- AE record
- medical history
- prior and concomitant medications

Also, the following documents are to be forwarded: any laboratory results, diagnostic test results, or medical reports relevant to the SAE. Subject's full names should be redacted from any documents that are not CRFs to protect the subject's identity. The subject initials and subject numbers should be added to these documents as identifiers.

E-mail/ E-Fax transmission is the preferred method to transmit SAE information. In rare circumstances and in the absence of e-mail capacity, notification by fax is acceptable.

If the investigator does not have all information regarding an SAE, he or she must not wait to receive additional information before notifying the sponsor of the event. The form must be updated when additional information is received. Follow-up information received on all SAEs must be forwarded to the sponsor by using the same procedure and timelines as for an initial report.

